13.3.3.1.2 Change from Baseline in DAS28-4(CRP)

For the change from baseline in DAS28-4(CRP) at Week 12, the linear mixed effect model for repeated measures will be applied. It includes treatment dose group (placebo, 100 mg, 200 mg, 300 mg VX-509) and visit as fixed effects, and subject as random effect, with adjustment of baseline DAS28-4(CRP) and prior anti-TNF use as covariates. The difference in DAS28-4(CRP) at Week 12 compared to placebo for each treatment group will be estimated. The corresponding 95% CI of the difference from placebo will be provided. A dose-response trend test will be performed at Week 12.

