8.2 Secondary Endpoints

- Proportion of subjects who achieve ACR50-CRP and ACR70-CRP responses at Week 12.
- Proportion of subjects with DAS28-4(CRP) <2.6, and those who achieve a remission, moderate response or good response according to the European League Against Rheumatism (EULAR) response criteria at Week 12.
- ACR hybrid scores at Week 12.

- Change from baseline in Health Assessment Questionnaire –Disability Index (HAQ-DI) at Week 12.
- Change from baseline in the Physical Function subscale of the 36-item Short Form (SF-36) at Week 12
- Change from baseline in the Physical Component and Mental Health Components of the SF-36 at Week 12
- Change from baseline in OMERACT RAMRIS synovitis, bone marrow edema (osteitis), erosion scores at Week 6.
- PK parameters of VX-509 and its metabolite in plasma (maximum observed concentration $[C_{max}]$ and area under the concentration versus time curve [AUC]).
- Safety and tolerability as indicated by adverse events, laboratory tests, electrocardiograms (ECGs) and vital signs.

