13.3.3.1.3 Change from Baseline in RAMRIS Scores

The revised OMERACT 5 RAMRIS will be used to score the designated hand and wrist for MRI scans in this study. ⁵² Two independent readers who are blind to dose assignment will score the MRIs and will subsequently reconcile any disparity by an adjudication meeting. The interreader and intrareader reliability coefficients based on RAMRIS scores at Week 12 will be calculated for RAMRIS synovitis, edema (osteitis), erosion and joint space narrowing scores. The definition of no progression of erosions from baseline at Week 12 (or end of study) will be an average change in RAMRIS erosion score ≤0.

Change from baseline for all 4 RAMRIS scores (synovitis score, osteitis score, erosion score, and joint space narrowing) at Week 12 will be analyzed separately. A similar linear mixed effect model for repeated measures will be applied. It includes treatment dose group (placebo, 100 mg, 200 mg, 300 mg VX-509) and visit as fixed effects, and subject as random effect, with adjustment of baseline RAMRIS score and prior anti-TNF use as covariates. The difference for these three scores at Week 12 compared to placebo for each treatment group will be estimated. The corresponding 95% CI of the difference from placebo will be provided.

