13.3.3.2 Analysis of Secondary Efficacy Variables

ACR50-CRP, ACR70-CRP response at Week 12

The response rate of the ACR50-CRP is defined as the subjects achieving an ACR50-CRP response divided by the total number of subjects included in the FAS, with a similar

definition for the ACR70-CRP. Non-responder imputation will be applied. The response rate at Week 12 will be summarized by the randomized treatment group and the 95% CI of the response rate difference for each treatment group compared to placebo will be calculated using the M&N method, a score-based interval.⁵³

Remission based on DAS28-4(CRP) at Week 12

Remission as defined by DAS score is DAS28-4(CRP) score lower than 2.6. The DAS remission rate will be assessed at Week 12. Non-responder imputation will be applied. The response rate at Week 12 will be summarized by the randomized treatment group and the 95% CI of the response rate difference for each treatment group compared to placebo will be calculated using the M&N method. 53

ACR Hybrid Scores at Week 12

The ACR hybrid score is designed to combine the ACR20, ACR50, and ACR70 response score with the mean % improvement in all of the 7 individual ACR components, and is a more sensitive measure of change. The % improvement or worsening in each component is limited to 100%. If the mean % improvement is ≥20% in a subject who did not meet ACR20 criteria, the ACR hybrid score is limited to 19.99; similarly for ACR50 and ACR70. Conversely, if the mean % improvement is <20% in a subject who met ACR20 criteria, the ACR hybrid score is 20.00; similarly for ACR50 and ACR70.

For the change from baseline of ACR hybrid score, the linear mixed effect model for repeated measures will be applied. It includes treatment dose group and visit as fixed effects, subject as random effect, with adjustment of baseline ACR hybrid score and prior anti-TNF use as covariates. The difference of ACR hybrid score for each treatment group comparing to placebo at Week 12 will be estimated. The corresponding 95% CIs of the differences from placebo will be provided.

Change from Baseline in Physical Function at Week 12

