Physical Function is assessed using the HAQ-DI and the Physical Function subscale of the SF-36. The following analyses apply to both. The linear mixed effect model for repeated measures will be applied. It includes treatment dose group and visit as fixed effects, subject as random effect, with adjustment of baseline scores and prior anti-TNF use as covariates. The difference of scores for each treatment group comparing to placebo at Week 12 will be estimated. The corresponding 95% CIs of the differences from placebo will be provided.

Change from Baseline in Physical Component Summary (PCS) score and Mental Component Summary (MCS) score from the SF-36, at Week 12

For the change from baseline for PCS score and MCS score at Week 12, the linear mixed effect model for repeated measures will be applied. It includes treatment dose group (placebo, 100 mg, 200 mg, 300 mg VX-509) as main effect, with adjustment of baseline scores and prior ant-TNF use as covariates. The difference of scores for each treatment group comparing to placebo at Week 12 will be estimated. The corresponding 95% CIs of the differences from placebo will be provided.

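### With no treatment-by-visit term, the repeated-measures models report an average over visits as the Week 12 difference from placebo

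*Protocol*

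**What the plan says.** All references are to the protocol.

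- **DAS28-4(CRP), 13.3.3.1.2.** The model has dose group "and visit as fixed effects, and subject as random effect, with adjustment of baseline DAS28-4(CRP) and prior anti-TNF use as covariates". The target follows: "The difference in DAS28-4(CRP) at Week 12 compared to placebo for each treatment group will be estimated". A dose-response trend test at Week 12 is also planned.
- **RAMRIS, 13.3.3.1.3.** The structure is the same: dose group "and visit as fixed effects, and subject as random effect, with adjustment of baseline RAMRIS score and prior anti-TNF use as covariates". The target is again Week 12: "The difference for these three scores at Week 12 compared to placebo for each treatment group will be estimated".
- **ACR hybrid, 13.3.3.2.** "It includes treatment dose group and visit as fixed effects, subject as random effect, with adjustment of baseline ACR hybrid score", plus prior anti-TNF use. HAQ-DI and SF-36 Physical Function have the same list with their own baseline scores.
- **SF-36 PCS and MCS, 13.3.3.2.** The model is called a repeated-measures model, but the listed terms are fewer: "It includes treatment dose group (placebo, 100 mg, 200 mg, 300 mg VX-509) as main effect, with adjustment of baseline scores", plus prior anti-TNF use. Neither visit nor subject is named.

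No treatment-by-visit interaction appears in any of these models.

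Section 8.1 defines DAS28-4(CRP) and three RAMRIS scores, four of the five primary endpoints, as change at Week 12. Section 8.2 makes an earlier RAMRIS time point a separate secondary endpoint: "Change from baseline in OMERACT RAMRIS synovitis, bone marrow edema (osteitis), erosion scores at Week 6".

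**The concern.** The listed terms and the stated target do not match. A model with additive dose and visit effects has a single drug-placebo difference, and asking it for the Week 12 difference returns that single number. The result describes the average effect over the treatment period, while the endpoint is the effect at its end.

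Section 13.1 says the study is not powered for comparisons with placebo, so its main product is estimates and intervals. It also says the RAMRIS dose-ranging information will be used to select the Phase 3 dose(s). If doses differ in how fast they act, pooling over visits can distort the comparison between them. Section 13.3.4.7 allows an interim analysis by the same methods once all subjects have completed Week 6. At that point a Week 12 figure from the additive model would rest largely on earlier visits.

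**Working it through.** **The protocol's own figures.** None depends on these models. The section 13.1 figures reproduce and are unaffected: power for 25% against 65% with 10 per arm is 24.5% by a two-sided Fisher test at an assumed alpha of 0.05 (stated: about 25%), and the RAMRIS sizes come out at 29, 99 and 1651 per arm (stated: 30, 100 and 1650).

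**Visits entering each model (Table 3-2, on treatment, after baseline).**
- Joint counts, global assessments and HAQ-DI: Weeks 2, 6, 8 and 12.
- MRI: Weeks 6 and 12.
- SF-36: Weeks 6 and 12.

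**Algebra.** As listed, the expected change for arm a at visit v is

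E[change] = arm(a) + visit(v) + covariates.

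Subtracting placebo at the same visit leaves arm(a) − arm(placebo), in which v does not appear. With complete data and a random subject intercept, the estimate is the equal-weight mean of the visit-specific differences. With missing visits the weights change, but there is still one number for all visits.

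**Check on simulated data (300 mg against placebo, assumed effects).** Each data set was fitted as the protocol lists the model and again with treatment-by-visit.
- DAS28, 2000 per arm. With the interaction: −0.2664, −0.7724, −0.9592, −1.1860 at Weeks 2, 6, 8, 12; the mean is −3.184/4 = −0.796. As listed: −0.796 at every visit.
- RAMRIS, 10 per arm. With the interaction: −0.9788 and −2.5569 at Weeks 6 and 12; the mean is −1.768. As listed: −1.768 at both.

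**Size of the bias.** The protocol gives no effect by visit. These shapes are assumptions, scaled to a largest difference of 1:

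| Assumed difference by visit | True Week 12 | Pooled | Error |
|---|---|---|---|
| 0.8, 1, 1, 1 (early plateau, four visits) | 1.00 | 3.8/4 = 0.95 | 5% too small |
| 0.3, 0.7, 0.85, 1 (still growing, four visits) | 1.00 | 2.85/4 = 0.7125 | 29% too small |
| 0.5, 1 (linear from baseline, Weeks 6 and 12) | 1.00 | 1.5/2 = 0.75 | 25% too small |
| 1, 1, 1, 0.8 (waning, the plateau reversed) | 0.80 | 3.8/4 = 0.95 | 0.95/0.80 = 1.19, so 19% too large |

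**Width of the interval.** For m visits with equal variance and within-subject correlation ρ, the standard error of the pooled difference relative to that of a single-visit difference is sqrt(ρ + (1 − ρ)/m). The protocol gives no ρ, so a range is shown:

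| ρ (assumed) | m = 2 | m = 4 |
|---|---|---|
| 0.3 | sqrt(0.650) = 0.81 | sqrt(0.475) = 0.69 |
| 0.5 | sqrt(0.750) = 0.87 | sqrt(0.625) = 0.79 |
| 0.8 | sqrt(0.900) = 0.95 | sqrt(0.850) = 0.92 |

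A simulation with 10 per arm, SD 1.2 and ρ = 0.55 gave standard errors of 0.44 (as listed) and 0.54 (with interaction), a ratio of 0.81. The formula with m = 4 gives sqrt(0.6625) = 0.81.

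**The case against.** The best defence is that the protocol states its intent. It asks for Week 12 differences throughout, the verb introducing the terms can be read as non-exhaustive, and section 13.3 leaves methodological detail to the SAP, where interactions and covariance structure are often settled. This would carry weight had the protocol left the model open. It did not: it gives fixed effects, random effect and covariates, and repeats the list for several endpoints. A model specified to that level and followed as written misses its target.

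A second defence is efficiency. With 10 per arm, pooling is more precise, and its narrower interval is valid if the effect is constant over visits. That is correct, but the protocol states neither that assumption nor an average-effect target.

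It also stands that ACR20-CRP is analysed at Week 12 alone, and that section 13.3.1 provides summaries by scheduled time point, so visit-specific data would remain visible.

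Four stronger readings are tempting but not supported:
- **That the Week 6 and Week 12 RAMRIS results must coincide.** Section 13.3.3.1.3 applies its model to Week 12, and no model is named for Week 6. They coincide only if Week 6 is read from that model, the only RAMRIS model given.
- **That the Week 12 effect is necessarily understated, by some fixed percentage.** Size and direction depend on a time course the protocol does not give. Section 6.4 describes rapid improvement in signs and symptoms with other JAK inhibitors, so an early plateau with small bias is plausible for clinical measures.
- **That the PCS/MCS model is a worse error.** Its repeated-measures label implies visit and subject, and the preceding paragraph lists both. It looks like abbreviated drafting.
- **That the off-drug Safety Follow-up Visit is in the average.** Table 3-2 collects the clinical measures there, but nothing puts that visit in the model.

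**Conclusion.** The point holds. Followed as written, the models for DAS28-4(CRP), RAMRIS, ACR hybrid, HAQ-DI and SF-36 Physical Function do not estimate a Week 12 difference. They estimate one pooled over Weeks 2, 6, 8 and 12 (DAS28, HAQ-DI, ACR hybrid) or over Weeks 6 and 12 (RAMRIS, SF-36). That part is algebra and needs no assumption beyond taking the listed terms as the model.

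The numerical consequence does rest on assumption: from about 5% too small (early plateau) to 25 to 30% too small (effect growing to Week 12), and too large if the effect wanes. The standard error is roughly 0.7 to 0.95 of that for a Week 12 contrast across the correlations tried, so the interval is too narrow for Week 12 unless the effect is constant.

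This should be corrected before analysis, because the models serve four of the five primary endpoints and RAMRIS informs Phase 3 dose selection.

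**What to change.** In 13.3.3.1.2, 13.3.3.1.3 and 13.3.3.2:
- Add treatment-by-visit to each repeated-measures model.
- Take the Week 12 difference from placebo, and the DAS28 dose-trend test, from the Week 12 cell means.
- Take the Week 6 RAMRIS secondary endpoint from the Week 6 cell means of the same model.
- Give PCS and MCS the same structure: visit, treatment-by-visit and within-subject correlation.
- State that only on-treatment visits enter the models.

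This takes about a sentence per section. It needs no new data and leaves the figures in 13.1 unchanged. The price is somewhat wider intervals: in the DAS28 simulation above, a standard error of 0.54 instead of 0.44. If an average effect over the treatment period is also of interest, it can be reported from the same model under that name.

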13.3.3.1.3 Change from Baseline in RAMRIS Scores

The revised OMERACT 5 RAMRIS will be used to score the designated hand and wrist for MRI scans in this study. ⁵² Two independent readers who are blind to dose assignment will score the MRIs and will subsequently reconcile any disparity by an adjudication meeting. The interreader and intrareader reliability coefficients based on RAMRIS scores at Week 12 will be calculated for RAMRIS synovitis, edema (osteitis), erosion and joint space narrowing scores. The definition of no progression of erosions from baseline at Week 12 (or end of study) will be an average change in RAMRIS erosion score ≤0.

Change from baseline for all 4 RAMRIS scores (synovitis score, osteitis score, erosion score, and joint space narrowing) at Week 12 will be analyzed separately. A similar linear mixed effect model for repeated measures will be applied. It includes treatment dose group (placebo, 100 mg, 200 mg, 300 mg VX-509) and visit as fixed effects, and subject as random effect, with adjustment of baseline RAMRIS score and prior anti-TNF use as covariates. The difference for these three scores at Week 12 compared to placebo for each treatment group will be estimated. The corresponding 95% CI of the difference from placebo will be provided.

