9 STUDY DESIGN

9.1 Overview of Study Design

This is a Phase 2, randomized, placebo-controlled, double-blind, dose-ranging, multicenter study of VX-509 in subjects with moderate to severe RA who are seropositive or have demonstrated erosive disease, and an inadequate response to a DMARD.

Subjects who have been on a stable dose of DMARD (Section 10.3) must have a swollen joint count of ≥ 6 out of 66 assessed joints and a tender joint count of ≥ 8 out of 68 assessed joints, and a CRP level $\geq 1.2 \times$ the upper limit of normal (ULN) or Westergren erythrocyte sedimentation rate $\geq 1.2 \times$ ULN to qualify for the trial. MRI of the most swollen hand (2+ synovitis of wrist or ≥ 2 MCPs) at baseline will be performed before dosing and at Weeks 6 and 12. A subset of approximately 6 (no more than 10) subjects will undergo arthroscopic synovial biopsies before the first dose at baseline (Day 1) and at Week 4 (Synovial Biopsy Subset).

Subjects will be randomized with stratification based on prior use of biological response modifiers (including a tumor necrosis factor [TNF] inhibitor). VX-509 will be coadministered with DMARD for a planned duration of 12 weeks. Approximately 40 subjects will be randomized to 1 of 4 dosing regimens at a 1:1:1:1 ratio. VX-509-matched placebo tablets will be used to maintain the double-blind. As an exception, the subjects in the Synovial Biopsy Subset will only be randomized to the 200 mg qd dose of VX-509 (Arm C). Subjects in the Synovial biopsy Subset will know that they are not receiving placebo, but not the dose they are receiving.

Arm A. Placebo (N = 10)
Arm B. 100 mg VX-509 qd (N = 10)
Arm C. 200 mg VX-509 qd (N = 10)
Arm D. 300 mg VX-509 qd (N = 10)

The protocol has optional interim analyses (IA) for the purpose of selecting appropriate dose(s) for a subsequent pivotal trial (Section 13.3.4.7). No changes in study design or conduct will be made based on the results of an IA.

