11.4 Method of Assigning Subjects to Treatment Groups

Each subject will be assigned a unique screening number by the study site before evaluation of inclusion and exclusion criteria at screening. Subjects who satisfy inclusion and exclusion criteria will receive a unique subject number on Day 1, before the first dose, according to a predetermined randomization schedule.

Personnel at the study site will contact the interactive voice/web response system (IVRS/IWRS) for subject enrollment and randomized treatment assignment. The IVRS/IWRS will assign subjects at a ratio of 1:1:1:1 to 1 of the 4 treatment groups, with stratification based on previous use of any biologic response modifier drug (including anti-TNF) for RA. The subjects who additionally undergo synovial biopsy will be an exception and will only be randomized to Arm C.

The randomly assigned subject number in the IVRS/IWRS will be used to identify the individual subject for the duration of the study. Appropriate study drug will be dispensed for each subject based on the randomization information from IVRS/IWRS.

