13.3.2.3 Demographics and Baseline Characteristics

Demographic and baseline characteristics will be summarized by FAS. Demographics will include age, gender, race, weight, height, BMI, region (United States, Other). Baseline characteristics will include duration of RA, DAS28-4(CRP), tender joint count, swollen joint count, CRP, ESR, rheumatoid factor (RF) (negative/positive), anti-CCP antibody status (negative/positive), RF and CCP status (RF+/CCP+, RF+/CCP-, RF-/CCP+, RF-/CCP-), current smoking status, HAQ-DI, subject assessment of pain, subject global assessment, physician global assessment, prior biologic response modifier (including anti-TNF) use (yes/No), previous number of DMARDs used (biologic + nonbiologic), baseline erosion status (yes/No), baseline vdHmTSS, and baseline RAMRIS scores (synovitis score, bone marrow edema (osteitis), erosion score, joint space narrowing score).

Continuous variables will be summarized by descriptive summary statistics and categorical variables will be summarized by counts in each category. For the RF and CCP status summary, if there is missing information, it will be considered as negative status. Duration of RA is defined as number of months between date of RA diagnosis and date of randomization. If day of diagnosis is missing, 15th day of the month will be used for duration calculation. If month is missing, July 1st of the diagnosis year will be imputed for the duration calculation.

Medical history will be presented in a subject data listing for condition/diagnosis and each medical history condition will be recorded as ongoing or not on the date of informed consent.

No statistical tests will be carried out to evaluate any baseline imbalance between dose groups.

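### Randomisation is stratified by any prior biologic, but the mixed models adjust for prior anti-TNF use only; the cost is a little precision and the correction is a wording change

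*Protocol*

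**What the plan says.** Section 11.4 describes a central assignment system that allocates 1:1:1:1 "with stratification based on previous use of any biologic response modifier drug (including anti-TNF) for RA". Section 9.1 gives the same factor and again treats TNF inhibitors as one part of the class. There is one exception: "The subjects who additionally undergo synovial biopsy will be an exception and will only be randomized to Arm C".

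The analysis sections name a different variable:

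- Section 13.3.3.1.2, DAS28-4(CRP): "with adjustment of baseline DAS28-4(CRP) and prior anti-TNF use as covariates".
- Section 13.3.3.1.3, all four RAMRIS scores: "with adjustment of baseline RAMRIS score and prior anti-TNF use as covariates".
- Section 13.3.3.2, ACR hybrid score: "with adjustment of baseline ACR hybrid score and prior anti-TNF use as covariates". The HAQ-DI, SF-36 Physical Function, PCS and MCS models in the same section carry the same anti-TNF covariate.

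The baseline table in Section 13.3.2.3 uses the wide definition: "prior biologic response modifier (including anti-TNF) use (yes/No" is how the variable is listed there. The stratification variable is therefore planned for collection and display, but no efficacy model uses it.

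**The concern.** An analysis normally carries the factor that restricted the randomisation. If that factor predicts outcome and is left out, the variance it explains stays in the error term and the model standard errors do not quite reflect the design.

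Here the covariate is a subset of the stratum rather than the stratum itself. It places subjects who had only non-TNF biologics together with subjects who never had a biologic. The mismatch runs through the models for four of the five primary endpoints (DAS28-4(CRP) and RAMRIS synovitis, osteitis and erosion). The trial has about 10 subjects per arm, and Section 13.1 says its RAMRIS dose-ranging results will inform the choice of Phase 3 doses, so even small losses of precision are worth avoiding when avoiding them is free.

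**Working it through.** **Can the two variables differ in this trial?** Yes. The washout table in Section 16.2 lists abatacept, anakinra, rituximab/ocrelizumab and tocilizumab alongside the TNF inhibitors, and exclusion 22 in Section 10.2 admits earlier users of depleting antibodies once cytopenias have recovered. Section 10.3 also treats TNF inhibitors as part of the biologic DMARDs. No section says that prior anti-TNF use stands for any prior biologic. The disagreement goes one way only: every anti-TNF user is in the yes stratum, but not every yes subject is an anti-TNF user.

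**Does any figure in the plan depend on it?** No. The power of about 25% in Section 13.1 (ACR20-CRP, 25% versus 65%, 10 per arm) reproduces as 24.5% with a two-sided Fisher exact test at 0.05 (the level is assumed) and involves no covariate.

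**Inputs.** N = 40 comes from Section 9.1. The following are assumptions, because the documents do not give them:

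- q, the share with any prior biologic: 0.30 to 0.50.
- f, the share of those who had non-TNF agents only: 0.10 to 0.25.
- R², the share of outcome variance explained by the stratum: 5% to 10%.

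**Formulas.** Subjects coded against their stratum = 40 × q × f.

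Let A be any prior biologic (probability q) and T prior anti-TNF use (probability q(1−f)), with T a subset of A. Then Cov(A,T) = q(1−f)(1−q), Var(A) = q(1−q) and Var(T) = q(1−f)[1−q(1−f)], so

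r² = (1−f)(1−q) / [1−q(1−f)].

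If anti-TNF use relates to outcome only through the stratum, it captures a fraction r² of the stratum effect. Replacing it by the stratum recovers R² × (1−r²) of outcome variance.

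| q | f | Subjects miscoded | r² | Recovered, R² = 5% | Recovered, R² = 10% |
|---|---|---|---|---|---|
| 0.30 | 0.10 | 1.2 | 0.63/0.73 = 0.86 | 0.7% | 1.4% |
| 0.30 | 0.25 | 3.0 | 0.525/0.775 = 0.68 | 1.6% | 3.2% |
| 0.50 | 0.10 | 2.0 | 0.45/0.55 = 0.82 | 0.9% | 1.8% |
| 0.50 | 0.25 | 5.0 | 0.375/0.625 = 0.60 | 2.0% | 4.0% |

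**Effect on standard errors.** In the mildest row, residual variance falls from 1 − 0.05 × 0.86 = 0.957 to 0.950, and √(0.950/0.957) = 0.996, a reduction of about 0.4%. In the strongest row it falls from 1 − 0.10 × 0.60 = 0.94 to 0.90, and √(0.90/0.94) = 0.978, about 2%.

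**Outside the assumed range.** With q = f = 0.5, 10 subjects would be miscoded and r² would be 0.33. With f = 0 the two variables are identical and nothing is lost.

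**Arm C.** Section 9.1 puts about 6, and at most 10, biopsy subjects into Arm C, whose planned size is 10. The stratified draw cannot balance prior biologic use across arms for these subjects. In the main models the covariate is the only control of this factor for them. The sensitivity analysis without biopsy subjects (Section 13.3.3.4) names ACR20-CRP and DAS28-4(CRP), not RAMRIS.

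**The case against.** The strongest reply is that the effect is small and that the models do not ignore the stratum: they carry a correlated proxy for it. This stands. A reader might infer that the standard errors are simply wrong, or that the primary comparisons are biased. The documents do not support either reading. Among subjects allocated by the stratified draw, a narrower baseline covariate does not bias the treatment contrast, and any distortion of the standard error is small and usually conservative.

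A reader might also expect the switch to recover the full 5-10% of variance assumed for the stratum. That would be the gain over no adjustment at all, and anti-TNF use already captures most of it.

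It would also be tempting to say that the covariate pools patients in whom a non-TNF biologic had failed with biologic-naive patients. Sections 10.2 and 16.2 speak of discontinuation and washout, not of failure.

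Nor does the mismatch show a defect in the Miettinen-Nurminen intervals for the ACR responses. Sections 13.3.3.1.1 and 13.3.3.2 describe them without a covariate, which is a legitimate choice. Splitting 10 subjects per arm on a 30-50% factor would leave cells of about 3 to 7.

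Two further replies carry partial weight. The trial is stated not to be powered against placebo, so little turns on a 1-2% change in a standard error. The strata also do not govern the biopsy subjects, which weakens the argument from design for the 200 mg contrast. But that same fact makes the covariate matter more there, because nothing else in the main models controls the factor. Finally, Section 13.3 leaves methodological detail to the SAP, but the protocol itself names this covariate repeatedly and gives no reason for choosing a variable narrower than its own stratum.

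**Conclusion.** The inconsistency is real, explicit and present in every covariate-adjusted model the protocol describes. It is a modest point. On the stated assumptions, about 1 to 5 of 40 subjects are coded against their stratum, and using the stratum would recover about 0.7-4% of outcome variance. These sizes rest on an assumed prior-biologic mix, an assumed strength of the stratum, and anti-TNF use having no effect beyond the stratum. The mismatch does not invalidate the primary analysis or alter any stated sample size or power figure. It is worth correcting because the right variable is already planned and because, for the 200 mg arm, the covariate has to do work that the randomisation cannot.

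**What to change.** In Sections 13.3.3.1.2, 13.3.3.1.3 and 13.3.3.2, replace prior anti-TNF use by the stratum recorded in the IVRS/IWRS: prior biologic response modifier use, yes or no. If anti-TNF exposure is of separate interest, keep it as a covariate in a sensitivity analysis. Leave the Miettinen-Nurminen analyses as they are. The cost is a change of wording: the variable is already listed in Section 13.3.2.3, no new data are needed, and the sample size is unaffected.
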